5.2. Baseline Definitions

For 12-lead ECGs and vital signs, the baseline value will be the average (for quantitative assessments) or the worst case (for interpretation) of the triplicate pre-dose assessments within each period. For clinical laboratory parameters, the baseline value will be the latest pre-dose assessment with a non-missing value, including those from unscheduled

visits, prior to the first study drug administration in each treatment period. If there is no non-missing value prior to the first study drug administration in each treatment period, the last non-missing value in the previous treatment period will be defined as baseline..

Parameter	Study Assessments Considered as Baseline			Baseline Used in Data Display
	Screening	Day -1	Day 1 (Pre-Dose)	
Safety				
Vital Signs	X	X	X	Day 1 (Pre-Dose) ^[1] for each period
12-Lead ECG	X	X	X	Day 1 (Pre-Dose) ^[1] for each period
Hematology	X	X		Day -1 for each period ^[2]
Clinical Chemistry	X	X		Day -1 for each period ^[2]
Urinalysis	X	X		Day -1 for each period ^[2]

ECG = electrocardiogram.
 [1] The average (for quantitative assessments) or the worst case (for interpretation) of the pre-dose triplicate assessments will be used as the baseline.
 [2] Day -1 in periods 2 and 3 refers to the Day 7 of the previous period.

Unless otherwise stated, if baseline data is missing no derivation will be performed and baseline will be set to missing.

5.3. Other Considerations for Data Analyses and Data Handling Conventions

Other considerations for data analyses and data handling conventions are outlined in the appendices:

Section	Component
11.1	Appendix 1: Schedule of Activities
11.2	Appendix 2: Study Phases and Treatment Emergent Adverse Events
11.3	Appendix 3: Data Display Standards & Handling Conventions
11.3.3	Appendix 4: Derived and Transformed Data
11.5	Appendix 5: Reporting Standards for Missing Data
11.6	Appendix 6: Division of AIDS (DAIDS) Table for Grading the Severity of Adult and Pediatric Adverse Events
11.7	Appendix 7: Values of Potential Clinical Importance
11.8	Appendix 8: Abbreviations & Trade Marks
11.9	Appendix 9: List of Data Displays

6. STUDY POPULATION ANALYSES

6.1. Overview of Planned Study Population Analyses

The study population analyses will be based on the Screened, Randomized, or Safety population, unless otherwise specified.

Study population analyses including analyses of participant's disposition, protocol deviations (including inclusion/exclusion criteria deviations), demographic and baseline characteristics, prior and concomitant medications, and exposure and treatment compliance will be based on VH/GSK's Integrated Data Standards Library standards. Details of the planned displays are presented in Appendix 9: List of Data Displays.

7. PHARMACOKINETIC ANALYSES

7.1. Primary Pharmacokinetic Analyses

7.1.1. Endpoint / Variables

7.1.1.1. Drug Concentration Measures

Refer to Appendix 3: Data Display Standards & Handling Conventions (Section 11.3.3 Reporting Standards for PK). Plasma concentrations of GSK3640254 and DTG will be measured and presented in tabular form and will be summarized descriptively. Plasma GSK3640254 and DTG concentration-time data will be listed by participant, treatment group, and sampling time for each study part and summarized by treatment group and sampling time for each study part.

7.1.1.2. Derived Pharmacokinetic Parameters

Pharmacokinetic parameters will be calculated by standard non-compartmental analysis according to current working practices and using the currently supported version of WinNonlin (8.0 or higher). All calculations of non-compartmental parameters will be based on actual sampling times. Pharmacokinetic parameters listed will be determined from the plasma concentration-time data, as data permit. Participants who experience emesis at or before 2 times median Tmax or participants whose pre-dose concentrations are >5% of their Cmax value for the given treatment will be excluded from the calculation of summary statistics and statistical analysis for the respective treatment.

Parameter	Parameter Description
AUC(0-∞)	Area under the plasma concentration-time curve from time 0 extrapolated to infinity, to be calculated using the linear trapezoidal rule for each incremental trapezoid and the log trapezoidal rule for each decremental trapezoid.
AUC(0-t)	Area under the plasma concentration-time curve from time 0 to the last quantifiable concentration, to be calculated using the linear trapezoidal rule for each incremental trapezoid and the log trapezoidal rule for each decremental trapezoid.
Cmax	Maximum observed concentration, determined directly from the concentration-time data.

NOTES:

- Additional parameters may be included as required.

7.1.2. Summary Measure

Pharmacokinetic parameters AUC(0-∞), AUC(0-t), and Cmax of GSK3640254 and DTG following single dose administration of GSK3640254 and DTG administered together as single agents and following single dose administration of FDC tablet formulations of GSK3640254 / DTG to healthy participants.

7.1.3. Population of Interest

The primary PK analyses will be based on the PK concentration population for plasma PK concentrations and the PK parameter population for plasma PK parameters and statistical analysis.

7.1.4. Statistical Analyses / Methods

Details of the planned displays are provided in Appendix 9: List of Data Displays and will be based on GSK Data Standards and statistical principles.

Unless otherwise specified, endpoints / variables defined in Section 7.1.1 will be summarized using descriptive statistics and listed.

Primary plasma PK parameters (AUC[0- ∞], AUC[0-t], and Cmax) will be estimated for GSK3640254 and DTG. Summary statistics (arithmetic mean, geometric mean, median, standard deviation [SD], coefficient of variation [CV], minimum, maximum, between-subject coefficient of variation [CVb], and 95% confidence interval [CI]) for plasma GSK3640254 and DTG PK parameter values will be summarized by treatment for each study part.

Summary statistics (arithmetic mean, 95% CI, SD, median, minimum, and maximum) for plasma GSK3640254 and DTG PK concentrations will be summarized by treatment using the PK Concentration Population.

7.1.4.1. Statistical Methodology Specification

The following PK statistical analyses will only be performed if sufficient data are available (i.e., if participants have well defined plasma profiles).

Endpoint / Variables

 Plasma primary PK endpoints include AUC(0-∞), AUC(0-t), and Cmax for GSK3640254 and DTG as data permit.
Model Specification

Part 1
 
 Analysis will be performed to compare the relative BA of 2 FDCs of GSK3640254 and DTG with GSK3640254 and DTG administered together as single agents. Analyses will be performed on the natural logarithms of AUC(0-∞), AUC(0-t), and Cmax using linear -mixed effect models with treatment, period, and sequence as fixed effects and participant nested within a sequence as a random effect. Effects will be estimated, and CIs will be constructed for the following treatment comparisons: 
 Treatment B (test) versus Treatment A (reference) Treatment C (test) versus Treatment A (reference) Point estimates, 90% CIs, and intra-subject CV% for treatment differences on the log scale derived from the model will be exponentiated to obtain estimates for geometric mean ratios and CIs on the original scale.

Part 2
 
 Analysis will be performed to compare the effect of food (-high fat and calorie meal) on the PK of GSK3640254 and DTG following administration of the selected FDC tablet formulation from Part 1. Analyses will be performed on the natural logarithms of AUC(0-∞), AUC(0-t), and Cmax using linear mixed-effect models with treatment, period, and sequence as fixed

effects and participant nested within a sequence as a random effect. Effects will be estimated, and CIs will be constructed for the following treatment comparisons: 
○ Treatment D (test) versus Treatment E (reference)○ Point estimates, 90% CIs, and intra-subject CV% for treatment differences on the log scale derived from the model will be exponentiated to obtain estimates for geometric mean ratios and CIs on the original scale
Model Checking & Diagnostics
• Model assumptions will be applied, but appropriate adjustments may be made based on the data.
Model Results Presentation
Part 1 
• Statistical analysis for comparison of GSK3640254 and DTG relative BA by analysis of variance (ANOVA) will be presented in tabular format with geometric mean ratios for the following treatment comparison:
○ Treatment B (test) versus Treatment A (reference)○ Treatment C (test) versus Treatment A (reference)
Part 2 
• Statistical analysis for the effect of food (high fat high calorie meal) by ANOVA will be presented in tabular format with geometric mean ratios for the following treatment comparisons:
○ Treatment D (test) versus Treatment E (reference)

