Part 2 will be dosed using a formulation selected from Part 1 based on PK data. Treatment D will be administered in the fed state. Participants will fast overnight for at least 10 hours prior to breakfast and will receive a high fat and calorie meal 30 minutes

prior to dosing. Participants will eat this meal in 25 minutes or less. Dose administration will occur within 5 minutes of completion of meal consumption. Participants will not receive any further food until 4 hours after dosing. Treatment E will be administered in the fasted state. Participants will fast overnight for at least 10 hours prior to dosing and until 4 hours after dosing.

In both Part 1 and Part 2, PK blood samples for the analysis of GSK3640254 and DTG will be collected prior to dosing (0 hour) on Day 1 and up to 96 hours post-dose in each period.

Safety and tolerability will be assessed by monitoring and recording of adverse events (AEs) and serious AEs (SAE), clinical laboratory test results, vital sign measurements, 12-lead electrocardiogram (ECG) results, and physical examination findings.

Study assessments will be performed as indicated in the Schedule of Activities (SoA; Section 1.3). For Part 1, study participants will be confined to the clinic from Day -2 of Period 1 until discharge on Day 5 of Period 3. For Part 2, study participants will be confined to the clinic from Day -2 of Period 1 until discharge on Day 5 of Period 2.

Brief Summary: A relative BA and food-effect study of the FDC of GSK3640254 / DTG in healthy participants. Study details include:

Part 1:

- Study Duration: 56 days (including screening)
- Treatment Duration: 3 days (Day 1 of each period)

Part 2:

- Study Duration: 49 days (including screening)
- Treatment Duration: 2 days (Day 1 of each period)

Number of Participants: For each part, approximately 18 participants will be enrolled to ensure that 14 evaluable participants complete the study.

Note: "Enrolled" means a participant's, or their legally acceptable representative's, agreement has been obtained to participate in a clinical study following completion of the informed consent process and screening. Potential participants who are screened for the purpose of determining eligibility for the study, but do not participate in the study, are not considered enrolled, unless otherwise specified by the protocol.

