6.1. Study Interventions Administered

In Part 1, all 3 treatments will be administered as per randomized treatment sequence. Based on Part 1 interim analysis, a treatment will be selected for administration in Part 2.

| Treatment | A | A | B | C |
|-------------------|------------|--------|-------------------------------|-------------------------------|
| Intervention Name | GSK3640254 | DTG | GSK3640254 / DTG (GSK4107821) | GSK3640254 / DTG (GSK4107821) |
| Type | Drug | Drug | Drug | Drug |
| Dose Formulation | Tablet | Tablet | Tablet | Tablet |

| Treatment | A | A | B | C |
|--------------------------------|---|--|---|---|
| Unit Dose Strength(s) | GSK3640254 25mg, 100 mg | DTG 50 mg | GSK3640254 / DTG, 150 mg/50 mg | GSK3640254 / DTG, 150 mg/50 mg |
| Dosage Level(s) | Single dose of 2 x GSK3640254 25mg Tablets + 1 x GSK3640254 100mg Tablet | DTG 50 mg | Single dose of 1 x GSK3640254 / DTG Tablet | Single dose of 1 x GSK3640254 / DTG Tablet |
| | Administered together as a single dose | | | |
| Route of Administration | Oral | Oral | Oral | Oral |
| Use | Experimental | Experimental | Experimental | Experimental |
| IMP and NIMP | IMP | IMP | IMP | IMP |
| Sourcing | GSK3640254 Sourced by Sponsor | DTG Sourced Locally | GSK3640254 / DTG Sourced by Sponsor | GSK3640254 / DTG Sourced by Sponsor |
| Packaging and Labeling | Provided in bulk by GSK. The investigator will package in high density polyethylene bottles. Each bottle will be labeled as required per country requirement. | 30 tablets in a HDPE bottle labelled per country requirement | Provided in bulk by GSK. The investigator will package in high density polyethylene bottles. Each bottle will be labeled as required per country requirement. | Provided in bulk by GSK. The investigator will package in high density polyethylene bottles. Each bottle will be labeled as required per country requirement. |

DTG = dolutegravir; FDC = fixed-dose combination; IMP = investigational medicinal product; NIMP = non investigational medicinal product.

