9.2. Sample Size Determination

As there is no formal research hypothesis being statistically tested in this study, the sample size was not selected based on statistical considerations but determined using feasibility. For each part, approximately 18 participants will be enrolled to ensure that 14 evaluable participants complete the study. If participants prematurely discontinue the study, additional participants may be enrolled after consultation with the sponsor to ensure that the required number of evaluable participants complete the study.

Note: "Enrolled" means a participant's, or their legally acceptable representative's, agreement has been obtained to participate in a clinical study following completion of the informed consent process and screening. Potential participants who are screened for the purpose of determining eligibility for the study, but do not participate in the study, are not considered enrolled, unless otherwise specified by the protocol.

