9.2.1. Sample Size Assumptions

Based on the results from a previous study ING113674 the intersubject coefficient of variation (CVb) for DTG was 27-34% and 30-35%, respectively, for AUC(0-∞) and Cmax in the fasted state and 31-35% and 19-24%, respectively in the fed state. Based on the results from a previous study 213567 the intersubject coefficient of variation (CVb) for GSK3640254 was 40.3% and 45.3%, respectively, for AUC(0-τ) and Cmax in the fasted state, and 42.2% and 35.6%, respectively in the fed state.

It was assumed that intrasubject coefficient of variation (CVw) was approximately 60% of the calculated CVb. Thus, it was decided that a conservative CVw estimate of 21% would be used for the sample size calculation for DTG and 27.2% would be a conservative estimate to use for the sample size calculation of GSK3640254.

Since it was expected that coadministration of GSK3640254 and DTG would increase the exposure of DTG, a range for point estimate for a ratio of 1.0, 1.1, and 1.2 were explored. It was expected that coadministration of GSK3640254 with DTG would have no significant impact on the exposure of GSK3640254, thus a range for point estimate for a ratio of 0.9, 1.0, and 1.1 were explored.

For DTG, with a sample size of 14, 16 and 18 evaluable participants, it was estimated that the precision (i.e., half-width of the 90% confidence interval [CI] on the log and ratio scale) and CI on the original scale for each point estimate would be as follows:

| N | Drug | CVw (%) | Half-Width (log scale) | Half-Width (original scale) | Point Estimate | 90% CI |
|----|------|---------|------------------------|-----------------------------|----------------|--------------|
| 14 | DTG | 21 | 0.139 | 0.149 | 1.0 | (0.87, 1.15) |
| | | | | | 1.1 | (0.96, 1.26) |
| | | | | | 1.2 | (1.04, 1.38) |
| 16 | DTG | 21 | 0.128 | 0.137 | 1.0 | (0.88, 1.14) |
| | | | | | 1.1 | (0.97, 1.25) |
| | | | | | 1.2 | (1.06, 1.36) |
| 18 | DTG | 21 | 0.120 | 0.127 | 1.0 | (0.89, 1.13) |
| | | | | | 1.1 | (0.98, 1.24) |
| | | | | | 1.2 | (1.06, 1.35) |

For GSK3640254, with a sample size of 14, 16 and 18 evaluable participants, it was estimated that the precision (i.e., half-width of the 90% CI on the log and ratio scale) and CI on the original scale for each point estimate would be as follows:

| N | Drug | CVw (%) | Half-Width (log scale) | Half-Width (original scale) | Point Estimate | 90% CI |

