9.4.1. Pharmacokinetic Analyses

Plasma GSK3640254 and DTG concentration-time data will be analyzed by PPD, under the oversight of the Clinical Pharmacology Modeling & Simulation Department within VH/GSK, using noncompartmental methods with Phoenix WinNonlin Version 8.0 or higher. Statistical analysis will be performed by PPD, under the oversight of Clinical Statistics, VH/GSK. Calculations will be based on the actual sampling times recorded during the study.

| Endpoint | Statistical Analysis Methods |
|----------|--|
| Primary | 
 The primary endpoints of this study are PK-related. The analysis for the primary PK endpoints will be performed for the PK Parameter |

| Endpoint | Statistical Analysis Methods |
|-----------|---|
| | 
Population. Plasma concentrations of GSK3640254 and DTG will be subjected to PK analyses using noncompartmental methods.
 
 Based on the individual concentration-time data the following primary plasma PK parameters will be estimated: 
 AUC(0-∞), AUC(0-t), and Cmax Analysis will be performed to compare the relative BA of 2 FDCs of GSK3640254 and DTG with GSK3640254 and DTG administered together as single agents. Analyses will be performed on the natural logarithms of AUC(0-∞), AUC(0-t), and Cmax using linear mixed-effect models with treatment, period, and sequence as fixed effects and participant as a random effect. Effects will be estimated, and CIs will be constructed for the following treatment comparison: 
 Treatment B versus Treatment A Treatment C versus Treatment A Point estimates and 90% CIs for treatment differences on the log scale derived from the model will be exponentiated to obtain estimates for geometric mean ratios and CIs on the original scale. The effect of food (moderate fat and calorie meal) on the PK of the select FDC of GSK3640254 + DTG will be similarly analyzed for the following treatment comparisons: 
 Treatment D versus Treatment E Summary statistics (arithmetic mean, geometric mean, median, standard deviation, minimum, maximum, and coefficient of variation) for plasma GSK3640254 and DTG primary PK parameter values will be summarized by treatment. |

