9.5. Interim Analysis

There will be no formal interim analysis. An analysis is planned after completion of Part 1 and will inform FDC formulation to include in Part 2. Preliminary safety & PK data will be analyzed by PPD under the oversight of Clinical Pharmacology Modeling & Simulation within VH/GSK.

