2.1. Changes to the Protocol Defined Statistical Analysis Plan

Changes from the originally planned statistical analysis specified in the protocol are outlined in Table 1.

Table 1 Changes to Protocol Defined Analysis Plan

Protocol	Reporting & Analysis Plan	
Statistical Analysis Plan	Statistical Analysis Plan	Rationale for Changes

 This is an open-label study 	
 Biostatistics and Programming teams from both GSK and PPD will remain blinded to the actual randomization schedule. Other teams including PPD Clinical Pharmacology team will remain open-label 	
 Biostatistics and Programming teams remain blinded following GSK's requirement

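### Does the Part 1 analysis need a direct bilayer-versus-monolayer (C/B) contrast because Part 1 also picks the tablet for Part 2?

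*SAP*

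**What the plan says.** The primary objective of Part 1 (Protocol 3; SAP 2.2) is the bioavailability of each FDC relative to the two drugs given together as single agents. The planned contrasts follow it. Protocol 9.4.1 lists B against A and "Treatment C versus Treatment A". SAP 7.1.4.1 repeats both in the model specification and in the results presentation, the second as "Treatment C (test) versus Treatment A (reference"). Neither document lists C against B.

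Part 1 has a second use. The Protocol synopsis says "Part 2 will be dosed using a formulation selected from Part 1 based on PK data". Protocol 6.1 says "Based on Part 1 interim analysis, a treatment will be selected for administration in Part 2", and Protocol 9.5 says "An analysis is planned after completion of Part 1 and will inform FDC formulation to include in Part 2". SAP 2.3 and 3.1 describe that step as a non-formal look at preliminary data with output from WinNonlin. They name no contrasts and give no numerical selection rule.

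On size, Protocol 9.2 states that "approximately 18 participants will be enrolled to ensure that 14 evaluable participants complete the study" in each part. No hypothesis is tested (Protocol 9.1; SAP 2.4).

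**The concern.** The candidates for Part 2 are B and C, so choosing between them seems to call for a comparison of B with C. The plan reports each against A and leaves the head-to-head ratio and its interval unprinted. A team that sees only B/A and C/A could take a chance difference between the tablets for a real one. The two planned estimates also share Treatment A. Someone who combined their intervals as if they were independent would get the wrong width for C/B. At stake would be the evidence behind the formulation carried into Part 2. The contrast would need no further participants or samples.

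**Working it through.** **Inputs.** Within-participant CV comes from Protocol 9.2.1: "a conservative CVw estimate of 21% would be used for the sample size calculation for DTG and 27.2% would be a conservative estimate" for GSK3640254. The sequences ABC, BCA and CAB in 1:1:1 ratio come from Protocol 4.1. The 90% CIs and the model (treatment, period, sequence, participant) come from SAP 7.1.4.1.

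Log-scale SD: σ = √ln(1 + CV²), which gives 0.2672 for GSK3640254 and 0.2077 for DTG.

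**The protocol's own figures.** Half-width = t(0.95, n − 1) × σ × √(2/n). At n = 14, t = 1.771 and √(2/14) = 0.378.
- GSK3640254: 1.771 × 0.2672 × 0.378 = 0.179
- DTG: 1.771 × 0.2077 × 0.378 = 0.139

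Both match Protocol 9.2.1. All 12 half-widths in Protocol 9.2.1 and 9.2.2 reproduce to within 0.001.

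**Precision of C/B with complete data.** On the log scale, C − B = (C − A) − (B − A), so the point ratio is C/A divided by B/A. In this design B − A and C − A have the same variance v and, because they share A, covariance v/2. Hence Var(C − B) = v + v − 2(v/2) = v, and C/B is exactly as precise as the two planned ratios. Least squares on the three-period design gives the same standard error for all three contrasts:

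| N (per sequence) | SE / σ | df | t | Half-width, GSK3640254 | Half-width, DTG |
|---|---|---|---|---|---|
| 14 (5/5/4) | 0.379 | 24 | 1.711 | 0.173 | 0.135 |
| 18 (6/6/6) | 0.333 | 32 | 1.694 | 0.151 | 0.117 |

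At N = 14 the 90% CI for C/B includes 1 when the observed ratio lies within exp(±0.173) = 0.84 to 1.19 (GSK3640254) or exp(±0.135) = 0.87 to 1.14 (DTG).

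**Precision with missing periods.** Assume 4 of 18 participants, taken at random, lack Period 3. There are C(18,4) = 3060 ways to choose them.

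| Split over sequences | Share | SE of C/B relative to B/A |
|---|---|---|
| 2/1/1 | 1620/3060 = 53% | −2.5% to +2.6% |
| 2/2/0 | 675/3060 = 22% | −3.9% to +4.1% |
| 3/1/0 | 720/3060 = 24% | −7.5% to +8.1% |
| 4/0/0 | 45/3060 = 1.5% | −12% to +14% |

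The +14% arises when all four are in ABC. The SE multiplier of C/B is then 0.380 against 0.333 for B/A, but C/A, which is reported, also has 0.380.

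**Is C/B the quantity that decides?** The documents do not say so. If the aim is to match the single agents, which is the Part 1 objective, B/A and C/A are the relevant figures and C/B can mislead. Take illustrative ratios B/A = 0.90 and C/A = 1.10. Then C/B = 1.10/0.90 = 1.22, with 90% CI 1.22 × exp(±0.173) = 1.03 to 1.45. The interval excludes 1 although both tablets are 10% away from the reference.

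**Which analysis informs the choice?** The contrasts in SAP 7.1.4.1 belong to the final analysis. SAP 3.2 starts that analysis after all participants have completed the study, and SAP 11.9.3 defines one deliverable, the final one, to which Table 3.13 and Figure 3.17 are assigned. A C/B row there would appear after Part 2 had been dosed. The choice itself rests on the post-Part 1 output of SAP 3.1, and nothing there limits that output to B/A and C/A or excludes C/B.

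**The case for a change.** The best argument for the concern is that neither document prints an interval for C/B and that SAP 3.1 leaves the contrasts of the post-Part 1 output unstated. A reader who works from the two printed intervals can also go wrong. Treating them as independent inflates the half-width by √2, at N = 14 by the protocol's formula to 0.179 × √2 = 0.253 for GSK3640254. Adding the contrast would cost one statement in a model already planned, and with no hypothesis tested it would spend no alpha.

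All of that is true, but it shows only that the contrast would be convenient. The √2 error is a reader's mistake and not a feature of the plan. The correct half-width is the one already printed for B/A and C/A, exactly with complete data and closely when missing periods are spread over the sequences. The final outputs also show the two tablets side by side: summaries by treatment with geometric means and 95% CIs (SAP 7.1.4 and 11.3.3) and concentration plots with A, B and C overlaid (Figures 3.9, 3.10, 3.13 and 3.14). One tablet goes forward whether or not a C/B interval includes 1, and no section says how such an interval would change the choice.

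**Conclusion.** The concern does not hold. The planned contrasts answer the stated Part 1 objective, no figure in the plan is wrong, and the analysis that informs the formulation choice is not confined to B/A and C/A. What goes unprinted is one interval. Its centre is the quotient of two reported ratios. With complete data its log half-width equals theirs: 0.173 (GSK3640254) and 0.135 (DTG) at N = 14, and 0.151 and 0.117 at N = 18. With four Period 3 values missing, the standard error stays within about 4% of that of B/A in the 2/1/1 and 2/2/0 splits, which are 75% of allocations (1620 + 675 = 2295 of 3060). Only the 1.5% of allocations with all four in one sequence can reach −12% or +14%.

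These sizes rest on the protocol's planning CVs, the three-sequence design and the assumed pattern of missing Period 3 data. The conclusion on substance rests on the documents giving no selection rule that requires B to be compared with C rather than each with A. A reader may prefer to see C/B printed, but its absence leads to no wrong or worse result.
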